## 3.2. Procedures for missing data

Missing data for teacher WEMWBS and PHQ-8 outcomes and student WEMWBS and SDQ outcomes (at baseline or at any follow-up) will be imputed using one or more appropriate imputation techniques depending on the patterns of missing data. If multiple imputation is used, imputation models will include all outcome timepoints (baseline and every follow-up), intervention arm, stratifying variables and a random effect for school to allow for clustering, as well as any appropriate baseline/ auxiliary covariates that are indicative of missingness.

## 3.3. Cluster effects

The analyses will take account of clustering by school and clustering due to repeated measures using random effects. If models fail to converge then robust standard errors (which account for intragroup correlation) will be used instead of random effects.

#### 3.4. Outliers

The data will be checked for validity, each variable will be examined separately, and any outliers (>3SD of the mean) will be checked for data entry errors. Where no error is identified, the variable will be checked for concordance with other variables (e.g. a high score on one measure of depression will be checked with a high score on another measure of depression), if they are different then it will be noted. We will also examine for influential observations in the main analysis models, and examine any such influential observations for outliers. All outliers detected will be taken into account during sensitivity analysis.

#### 3.5. Visit windows

Questionnaires at baseline, 12 months follow up and 24 months follow up will need to be returned within 12 weeks of initial date of questionnaire collection, otherwise they will not be included with in the study. Any questionnaires returned outside this window will be recorded as missing.

## 3.6. Definition

Data are missing at random (MAR) if, conditional upon the independent variables in the analytic model, the missing-ness depends on the observed outcomes of the variable being analysed but does not depend on the unobserved outcomes of the variable being analysed.

#### 4. DESCRIPTION OF PARTICIPANT CHARACTERISTICS

#### 4.1. Disposition

A flow of clusters through the trial will be summarised in a CONSORT diagram as appropriate for cluster trials that will include the eligibility, reasons for exclusion, numbers randomised to the two treatment groups, losses to follow up and the numbers analysed.

## 4.2. Baseline characteristics

Continuous data that are approximately normally distributed will be summarised in terms of the mean and standard deviation. Skewed data will be presented in terms of the medians and interquartile range. Categorical data will be summarised in terms of frequency counts and percentages. We will summarise all variables by trial arm, both cluster level and individual-level summary data will be provided by table 1, 2 and 3 (Section 8). We will also compare all variables by complete case status (i.e. between those who have all variables measured and those who have some missing outcomes).

## 5. ASSESSMENT OF STUDY QUALITY

## 5.1. Eligibility checks

The numbers of teachers and students completing the questionnaires, and reasons for exclusion, will be described.

## 5.2. Study completion

The final follow up is the questionnaire at T2, 24 months after baseline data collection.

## 5.3. Protocol deviations

## 5.4. Specify & justify changes made to the planned statistical analyses

## 6. ANALYSIS OF EFFECTIVENESS

## 6.1. Summary of primary and secondary outcomes

Primary outcome summary will be presented as given in table 5 (section 8), while the summary for secondary outcomes will be presented as shown in table 6 (section 8).

## 6.2. Primary analysis

The tested null hypothesis is that there is no difference in level of teacher wellbeing over the period of 2 years (i.e. repeated measures analysis, no primary timepoint) in schools with peer supporters that have MHFA training and those in schools that do not have such support. The primary analysis will be carried out under the intention to treat principle, analysing participants as randomised without the imputation of missing data.

- 1. The primary analysis: Repeated measures (random effects) models will be used to examine pattern of change in primary outcome over baseline, T1 and T2, adjusted for stratification variables, sex and years of experience. This will include a random effect for individual participants, and another for school. If models fail to converge, we will use robust standard errors to account for clustering at one of the levels. This model will include every teacher who has at least one measure of the outcome (i.e. at baseline, one or two year follow up). Using a maximum likelihood estimator this analysis is robust to data which are MAR [8, 9].
- 2. Results will be presented as mean difference in the primary outcome between the trial arms over the follow up period, with associated 95% confidence interval and p- value.

Assumptions and Links for each model:

The link function for this model will be the identity function, and the different model assumptions will be checked to ensure that the model is a good fit for the data. This will include, check for normality assumptions at the different levels, making sure that homoscedasticity holds, and checking that the assumption of linearity of change holds. If these assumptions do not hold, we will investigate transformations of the data to achieve normality. If the model does not converge, we will use a simpler random effects model accounting for clustering by school only.

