#### 2.7. Sample size and justification

The primary outcome measure will be the WEMWBS scale. A change of 3 points on this scale is close to the difference in mean scores between the highest and lowest ranked schools in the pilot study. The sample size takes account of clustering; in the pilot data from 6 schools, the WEMWBS ICC (calculated using the loneway command in Stata) for teachers was 0.01 (95%Cl 0.00, 0.05) [1]. We assume a mean of 50 teachers followed up per school after allowance for 20% dropout (with a coefficient of variation of sample size of 0.5), and an SD for WEMWBS of 8.4 (based on the pilot data). Given that estimates based on pilot data can be unreliable [2], assuming an ICC of 0.05, which is greater than that seen in the pilot, -a sample size of 24 schools (12 intervention and 12 control) would achieve over 80% power. This would rise to 98% if the ICC is 0.02, and fall to 68% for an ICC of 0.08. These estimates of power are likely to be conservative given that the sample size calculation does not account for the baseline assessment of the outcome.

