#### 2.8. Blinding and breaking of blind

Allocation to study arm will take place after baseline data are collected to ensure blinding among all parties during this first data collection. It is not possible for the schools, teachers or students to be blind to intervention status. The research assistants/associate leading the outcome data collection, will also be collecting the process data which will prevent blinding. The schools will however be assigned ID numbers and as such casual staff and the statisticians analysing the primary and secondary outcomes data will be blind to the schools' identities and intervention status. A timeline diagram of blinding status throughout the trial processes will be produced for clarification [3].

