## 2.10. Outcome measures

## 2.10.1. Primary outcome

The primary outcome is the average effect of the intervention on mental wellbeing of teachers over the duration of follow up, measured using the self-completed WEMWBS questionnaire [4] collected at baseline, one and two year follow ups. The WEMWBS scales from 14-70 and will be analysed as a continuous variable.

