## 6.3. Secondary analyses

The primary analysis (i.e. mixed effects repeated measures model including every teacher who has at least one measure of the outcome i.e. at baseline, one or two year follow up) will be repeated with a treatment by time interaction term added to the model. This will allow estimation of treatment effect at 12 and 24 month follow ups separately. Analysis of secondary outcomes will include linear, ordinal and logistic regression models dependent on the nature of the outcome variable being analysed (continuous, ordinal or binary respectively).

For secondary individual level outcomes that are measured at baseline, 12 and 24 months (e.g. PHQ-8), repeated measures models will be used, these models will include random effects for clustering by individual (due to repeated measure) and by school. All individuals with at least one observation of the outcome measure will be included in the model for that outcome measure using maximum likelihood under a Missing at Random (MAR) assumption. For each secondary individual level outcome that are measured at baseline, 12 and 24 months, 3 models will be presented:

- Model 1: Unadjusted model Repeated measures of the outcome regressed on treatment arm accounting for clustering due to repeated measures and by school (using random effects).
- Model 2: Partially adjusted model Model 1 plus adjustment for stratification variables.
- Model 3: Fully adjusted model Model 2 plus additional adjustment for covariates. For teacher based outcomes the covariates adjusted for will be sex and years of experience, for student based outcomes sex and ethnicity will be included as covariates.

For each secondary individual level outcome measured only at baseline and 24 months, 3 models will be presented:

- Model 1: Unadjusted model Outcome at 24 months regressed on treatment arm and baseline value of the outcome, accounting for clustering by school (using a random effect).
- Model 2: Partially adjusted model Model 1 plus adjustment for stratification variables.
- Model 3: Fully adjusted model Model 2 plus additional adjustment for covariates. For teacher based outcomes the covariates adjusted for will be sex and years of experience, for student based outcomes sex and ethnicity will be included as covariates.

For each secondary school level outcome measured only at baseline and 24 months, 2 models will be presented:

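### As written, the primary model averages the pre-allocation baseline wave into its single arm coefficient, so it does not estimate the follow-up effect and shrinks a true 3-point difference to 2.0 or less

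*SAP*

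**What the plan says.** Section 2.10.1 defines the primary outcome as the "average effect of the intervention on mental wellbeing of teachers over the duration of follow up". Section 6.2 item 2 likewise promises a between-arm mean difference over follow-up.

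Section 6.2 item 1 describes the model: "Repeated measures (random effects) models will be used to examine pattern of change in primary outcome over baseline, T1 and T2". It has random effects for teacher and for school, and the listed adjustments are the stratification factors, the teacher's sex and length of experience. On who is analysed it says: "This model will include every teacher who has at least one measure of the outcome (i.e. at baseline, one or two year follow up". Baseline WEMWBS is not among the listed covariates.

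Section 6.3 says the primary analysis "will be repeated with a treatment by time interaction term added to the model", in order to separate the 12- and 24-month effects. For the other teacher outcomes measured at three waves, Model 1 is: "Repeated measures of the outcome regressed on treatment arm accounting for clustering due to repeated measures and by school".

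On timing, section 2.8 says: "Allocation to study arm will take place after baseline data are collected". On power, section 2.7 says of its own figures: "These estimates of power are likely to be conservative", because the baseline measurement was left out of the calculation.

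**The concern.** A teacher with only a baseline score can contribute to this model only if baseline is an outcome row. If the interaction is something added later, the primary model carries a single arm term across all three waves. That term is a weighted average of the arm differences at baseline, T1 and T2, and the first of these is zero in expectation because no school has yet been allocated. The model in item 1 and the quantity reported under item 2 are then different things.

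The headline estimate and its confidence interval would be pulled towards zero, and power would fall below the design value. Baseline would also not serve as an adjustment. A chance baseline difference between the arms would enter the estimate directly, with weight one third in complete data, which matters with 24 schools.

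**Working it through.** **Inputs from section 2.7:** difference 3 points; SD 8.4; mean 50 teachers followed up per school after 20% dropout; CV of cluster size 0.5; ICC 0.05 (also 0.02 and 0.08); 12 schools per arm.

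**Assumptions, not in the SAP:** two-sided 5% test; within-teacher correlation r of 0.5 to 0.7; for steps 2 to 5, equal cluster sizes and a school effect constant over time.

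**1. The plan's own figures.** Design effect = 1 + ((CV² + 1)m − 1) × ICC. At ICC 0.05 this is 1 + (1.25 × 50 − 1) × 0.05 = 4.075. SE = 8.4 × √(2 × 4.075/600) = 0.979. A noncentral t with 22 df gives 83.4%. ICC 0.02 gives 97.7% and ICC 0.08 gives 68.1%. The stated values (over 80%, 98%, 68%) reproduce, but for an undiluted 3-point difference.

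**2. What the single coefficient estimates.** With complete data and random intercepts for school and teacher, the three waves have equal weight: (0 + 3 + 3)/3 = 2.0. This does not depend on the ICC, on r, or on whether time main effects are included. If the effect were 1.5 at T1 and 3 at T2, the coefficient would be (0 + 1.5 + 3)/3 = 1.5, against a true follow-up average of 2.25. The factor is again two thirds.

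**3. Power with complete data, ICC 0.05.** For T waves, variance = (2 × 8.4²/12) × [ICC + (r − ICC)/50 + (1 − r)/(50T)], and 2 × 8.4²/12 = 11.76.
- T = 3, r = 0.5: 11.76 × (0.05 + 0.009 + 0.00333) = 0.733; SE 0.856; power for 2.0 is 61%.
- T = 3, r = 0.7: 11.76 × (0.05 + 0.013 + 0.002) = 0.764; SE 0.874; power for 2.0 is 59%.

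**4. Power with dropout.** The plan's 20% loss means 50/0.8 = 62.5 teachers per school at baseline (62 used). Generalised least squares with known variance components, ICC 0.05:

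| Teachers at baseline, T1, T2 | r | Expected coefficient | SE | Power (t, 22 df) |
|---|---|---|---|---|
| 62, 56, 50 | 0.5 | 1.82 | 0.843 | 54% |
| 62, 56, 50 | 0.7 | 1.80 | 0.857 | 52% |
| 62, 50, 50 | 0.5 | 1.73 | 0.845 | 50% |
| 62, 50, 50 | 0.7 | 1.68 | 0.858 | 47% |

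The coefficient falls further because baseline-only teachers add information only about the wave with no effect.

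**5. Comparison with the follow-up waves only.** With T = 2 the expected coefficient is 3.0, the SE is 0.868 (r = 0.5) to 0.881 (r = 0.7), and power is 90–91%.

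**6. The remark about conservatism.** One wave with equal clusters has SE 8.4 × √(2 × (1 + 49 × 0.05)/600) = 0.901. Using three waves lowers this to 0.856–0.874, a gain of 3–5%, while the expected coefficient falls by a third. Entering baseline in this way costs power.

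**The case against.** The SAP prints no model equation, and item 1 does not list the arm and time terms. Section 2.10.1, section 6.2 item 2 and Table 5, which summarises the primary endpoint at T1 and T2 only, all point to a post-baseline contrast. If arm were coded zero for everyone at baseline there would be no dilution, and the extra term in 6.3 could be read as splitting one follow-up effect into two. This stands as evidence of intent. But such coding is itself an arm-by-time structure, which 6.3 presents as an addition, and Model 1 in 6.3 describes a plain regression on arm. Section 1 says the plan should allow others to run the analysis, and an analyst following 6.2 and 6.3 literally would fit the diluted model.

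A reader might infer that the test is invalid, or that a real effect would vanish from the report. Neither follows. With no effect at any wave the coefficient has expectation zero, so the test keeps its size. Section 6.3 and Table 8 also give separate T1 and T2 effects, although these are secondary and do not replace the primary result in Table 7.

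A reader might also apply the two-thirds factor to every three-wave secondary outcome. It was derived for linear models. For the binary and ordinal versions of PHQ-8, absence and presenteeism the direction should carry over, but the size was not computed.

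**Conclusion.** The point holds for the model as written: it does not estimate the quantity that 2.10.1 and 6.2 item 2 define. The figure of 2.0 for a true 3-point effect needs only complete data and random intercepts. The 1.7 to 1.8 under dropout, and power of 59–61% (complete) or 47–54% (dropout) at ICC 0.05, also rest on the assumed within-teacher correlation, the two attrition patterns and equal cluster sizes. Equal sizes favour the planned model, since unequal sizes raise the SE. Power falls short of the stated figure of over 80% in every case examined. The arithmetic in 2.7 is sound for an undiluted difference, but its claim to be conservative does not hold for this model. The harm is to the estimate, its confidence interval and power, and it should be corrected before the analysis is run.

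**What to change.** Rewrite section 6.2 item 1:
- Keep baseline, T1 and T2 WEMWBS as outcomes, with time as a three-level factor.
- Constrain the baseline mean to be equal across arms (no arm main effect), and define the primary effect as the average of the arm effects at T1 and T2.
- Add a school-by-time random effect. With a school intercept alone, the constrained model at ICC 0.05 and r = 0.6 gives an SE of about 0.36, against 0.87 for the follow-up waves alone. That precision is real only if school effects do not change over time; otherwise the SE is understated.

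State in 6.3 that the 12- and 24-month effects are the arm-by-T1 and arm-by-T2 terms. Use the same structure in Models 1 to 3 for PHQ-8, absence and presenteeism. Remove or reword the remark on conservatism in 2.7.

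Modelling T1 and T2 with baseline WEMWBS as a covariate is an alternative but not an equivalent. Unless missing baselines are handled, it drops teachers without a baseline score, whom 6.2 includes, and so changes the analysis population.

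The cost is SAP wording and model code; no new data are needed.

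### The treatment-by-time model in SAP 6.3 has no school-by-wave random effect, so 12- and 24-month effects taken relative to baseline would have standard errors that are too small

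*SAP*

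**What the plan says.** Section 6.2 fits a repeated-measures model to "examine pattern of change in primary outcome over baseline, T1 and T2". On correlation it says: "This will include a random effect for individual participants, and another for school". I read both as random intercepts, since no slope is mentioned. It names no treatment-by-time term. The result is a mean difference between arms "with associated 95% confidence interval and p- value".

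Section 6.3 then says that this model "will be repeated with a treatment by time interaction term added to the model", and gives the purpose: "This will allow estimation of treatment effect at 12 and 24 month follow ups separately". For the other outcomes measured at three waves, "these models will include random effects for clustering by individual (due to repeated measure) and by school", but the three models listed there regress the outcome on arm plus covariates, without an arm-by-time term.

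Section 3.3 gives the general rule: "The analyses will take account of clustering by school and clustering due to repeated measures using random effects". Robust standard errors are a fallback: "If models fail to converge then robust standard errors (which account for intragroup correlation) will be used instead of random effects".

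No section names a school-by-time effect, a random school slope or an unstructured school covariance over waves. The model checks in 6.2 cover normality, homoscedasticity and linearity of change. The sensitivity analyses in 6.4 cover missing data, late returns, outliers and protocol violations. Neither list would reveal schools drifting apart for reasons unrelated to treatment.

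**The concern.** A single school intercept implies that, apart from treatment, all school means move in parallel over two years. A change of head, an inspection or staff turnover can shift one school and not another. Such a shift is shared by every teacher in the school at that wave, but the planned model can only place it in the teacher-level residual.

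The school intercept cancels from any comparison of change between arms. What is left in the model's standard error then shrinks with the number of teachers, whereas the true uncertainty is limited by the 24 schools. Tests of a 12- or 24-month effect relative to baseline would reject too often and the intervals would be too narrow. A model that lacks a variance component will usually converge, so the robust fallback would not come into play.

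**Working it through.** **Inputs from SAP 2.7:** difference 3 points, SD 8.4 (variance 70.56), 12 schools per arm, 50 teachers followed up per school, coefficient of variation (CV) of size 0.5, design ICC 0.05, pilot ICC 0.01. Two-sided 5% is inferred from the 95% interval.

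**Assumed, not in the SAP:** within-teacher correlation 0.5-0.7 (autocorrelation of a teacher's deviation from the school mean) and school autocorrelation 0.8-1 (share of the school variance that is stable over waves).

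**1. The plan's own power.** The design effect is 1 + ((1 + CV²)m − 1) × ICC. At ICC 0.05 it is 1 + (62.5 − 1) × 0.05 = 4.075. The SE is √(2 × 70.56 × 4.075 / 600) = 0.979, and 3/0.979 = 3.06. A noncentral t with 22 df gives 83.4%. ICC 0.02 and 0.08 give 97.7% and 68.1%. These match the stated figures (over 80%, 98%, 68%), so the inputs are read correctly.

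**2. Formula for a change from baseline.** Split the school variance (ICC × 70.56) into a stable part and a school-by-wave part s_st² = (1 − autocorrelation) × ICC × 70.56. Let s_e² be the teacher-by-wave residual. For m teachers seen at both waves, the variance of a school's mean change is 2(s_st² + s_e²/m). The planned model pools s_st² into the residual and reports 2(s_e² + s_st²)/m. The true/model variance ratio is therefore

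(s_e² + m·s_st²) / (s_e² + s_st²).

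**3. One case in full.** ICC 0.05, school autocorrelation 0.9, within-teacher correlation 0.5, m = 50: s_st² = 0.1 × 3.528 = 0.353 and s_e² = 0.5 × (70.56 − 3.528) = 33.52. The variance ratio is (33.52 + 17.64)/(33.52 + 0.353) = 1.51, so the SE ratio is 1.23. Type I error is 2Φ(−1.96/1.23) = 11%.

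**4. Ranges.** The lower end of each range uses m = 50 with within-teacher correlation 0.5. The upper end uses m = 50 × (1 + 0.5²) = 62.5, which allows for unequal schools, with correlation 0.7.

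| ICC | School autocorrelation | True/model SE | Type I error |
|---|---|---|---|
| 0.05 | 1 | 1.00 | 5% |
| 0.05 | 0.9 | 1.23-1.44 | 11-17% |
| 0.05 | 0.8 | 1.42-1.76 | 17-26% |
| 0.01 | 0.9 | 1.05-1.10 | 6-7% |
| 0.01 | 0.8 | 1.09-1.19 | 7-10% |

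**5. Check with unequal schools and turnover.** This sandwich-variance calculation used 24 schools, about 48-49 teachers per wave, size CV 0.47, an assumed 60% of teachers present at all three waves, and within-teacher correlation 0.6. The true/model SE ratios were:

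| Estimate | ICC 0.05, autocorr. 0.9 | ICC 0.05, autocorr. 0.8 | ICC 0.01, autocorr. 0.9 | ICC 0.01, autocorr. 0.8 |
|---|---|---|---|---|
| Change from baseline, T1 | 1.30 | 1.54 | 1.06 | 1.13 |
| T1 effect, baseline means equal | 1.28 | 1.51 | 1.06 | 1.11 |
| Follow-up average minus baseline | 1.30 | 1.54 | 1.06 | 1.13 |
| Arm difference at T1 alone | 1.03 | 1.06 | 1.01 | 1.03 |
| One arm term over three waves | 1.00 | 1.00 | 1.00 | 1.00 |

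T2 results agree with T1 to within 0.01. At ICC 0.05, the model SE of 0.45 for change from baseline compares with a true SE of 0.58 (autocorrelation 0.9) or 0.70 (0.8). In the last row the school intercept absorbs the averaged drift, so nothing is lost.

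**The case against.** The strongest reply is that the SAP never calls the 12- and 24-month effects baseline-adjusted. Baseline enters as an outcome wave, and Table 8 lists teacher WEMWBS at T1 and at T2 as differences in means between arms. That fits an arm difference at each wave, where the understatement is 1-6% and type I error is at most about 6.4%. This stands, and it is why the point is conditional. It does not remove the point: the interaction coefficients and their test are contrasts between waves, allocation follows baseline collection (2.8), which makes an effect relative to baseline a natural choice, and the SAP does not fix which contrast it will report.

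A reader might infer from 6.2 that the primary result is understated too, and from 6.3 that the PHQ-8 and other three-wave models are. The documents do not support that. As written, these fit one arm term over all waves, for which the linear-model ratio is 1.00. The primary effect would be exposed only if it were estimated as a follow-up effect relative to baseline. The two-wave models that regress the 24-month value on baseline are not affected.

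A reader might also reach larger figures, such as 1.6-1.9 at ICC 0.05 and autocorrelation 0.8. Those need an effective size near 78, that is 62.5 teachers (50/0.8) inflated again by 1.25. The SAP plans on 50 followed up.

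Finally, the only ICC observed is 0.01, where the error is small. That is fair, but 2.7 itself declines to rely on the pilot value and plans on 0.05.

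**Conclusion.** The point holds in a limited form. The treatment-by-time model in 6.3 omits school-by-wave variation, and nothing else in the SAP would detect or correct for it. For effects or tests relative to baseline, or with baseline means constrained equal, the standard error is too small whenever school means do not move in parallel. The direction is firm; the size is not. It rests on two assumed correlations, on effective school size 50-62.5 and on a normal-approximation test. The error is material at the design ICC of 0.05, small at the pilot ICC, and nil at school autocorrelation 1. The arithmetic covers the linear WEMWBS model only.

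**What to change.** In the treatment-by-time model of 6.3, state which contrast gives the 12- and 24-month effects, keep time categorical, add a school-by-wave random effect and base tests on school-level degrees of freedom. Do the same in 6.2 only if the primary effect is to be estimated relative to baseline. If the component cannot be estimated, use school-level cluster-robust standard errors with a small-sample correction, and say that this takes precedence over the fallback in 6.2 to a simpler model with school clustering only.

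The cost is SAP wording, one more variance component from 24 schools, some added risk of non-convergence, and wider intervals when schools drift. If the component is estimated at zero, the random-effects structure reduces to the planned one.

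### The primary mixed model is fitted by maximum likelihood with 24 schools and no small-sample correction, so its p-value is likely too small and its confidence interval too narrow

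*SAP*

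**What the plan says.** Section 6.2 specifies a repeated-measures model with random effects for teacher and school, adjusted for the stratification variables, sex and years of experience. It reports a mean difference with 95% CI and p-value. The estimator is named in the sentence on missing data: "Using a maximum likelihood estimator this analysis is robust to data which are MAR [8, 9". Section 6.3 repeats it for individual outcomes measured at all three waves: "using maximum likelihood under a Missing at Random (MAR) assumption".

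Section 3.3 gives the fallback: "If models fail to converge then robust standard errors (which account for intragroup correlation) will be used instead of random effects". Section 2.7 sets the size: "a sample size of 24 schools (12 intervention and 12 control) would achieve over 80% power" at an ICC of 0.05, and power would "fall to 68% for an ICC of 0.08".

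The SAP does not mention REML, a t reference distribution, a degrees-of-freedom method or a correction for few clusters. Section 9.2, for the Stata code, shows only a heading in the text available.

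**The concern.** Schools are randomised, so the precision of a constant arm effect comes from variation between 24 schools. The model also estimates school-level terms. With an intercept, arm, region (two levels) and free-school-meal level (three levels) there are five, which leaves 19 degrees of freedom.

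Two things then go wrong in the same direction. Maximum likelihood estimates the school variance without allowing for those five parameters, so the standard error is too small. A Wald z test then treats that variance as known. At stake are the single primary p-value and interval, and those of the three-wave secondary outcomes.

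**Working it through.** **Inputs from SAP 2.7:** 24 schools, 12 per arm; difference 3 ("A change of 3 points on this scale"); "an SD for WEMWBS of 8.4 (based on the pilot data"); mean cluster size 50 ("We assume a mean of 50 teachers followed up per school after allowance for 20% dropout"), coefficient of variation 0.5; planning ICC 0.05; pilot ICC 0.01 (95% CI 0.00 to 0.05). Strata are from 2.6. Two-sided 5% is inferred from the 95% CI in 6.2.

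**Step 1: reproduce the stated power.** Design effect = 1 + ((1 + 0.5²) × 50 − 1) × ICC = 1 + 61.5 × ICC. Standard error = 8.4 × √(2 × design effect / 600).

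| ICC | Design effect | SAP | Normal approximation | t, 22 df |
|---|---|---|---|---|
| 0.05 | 4.075 | over 80% | 86.5% | 83.4% |
| 0.02 | 2.23 | 98% | 98.5% | 97.7% |
| 0.08 | 5.92 | 68% | 72.0% | 68.1% |

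A t reference on 24 − 2 = 22 df reproduces all three figures. The normal approximation misses the last by 4 points.

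**Step 2: closed form for the planned test.** In a balanced design with five school-level parameters, and the school variance estimated above zero, maximum likelihood divides the between-school sum of squares by 24 where 19 is unbiased. The Wald z test therefore rejects when |t₁₉| > 1.96 × √(19/24) = 1.744, which has probability 9.7%. The correct interval uses 2.093, so it is wider by (2.093/1.96) × √(24/19) = 1.20.

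**Step 3: simulation under the null, five school-level parameters.** The balanced column uses 24 schools of 50. The unequal columns use cluster sizes with mean 50 and coefficient of variation 0.5, with 4,000 runs per cell (simulation error about ±0.9 points near 10%).

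| ICC | ML + z, balanced | ML + z, unequal | ML + t₁₉, unequal | REML + t₁₉, unequal |
|---|---|---|---|---|
| 0 | 4.8% | – | – | – |
| 0.005 | 6.7% | – | – | – |
| 0.01 | 8.1% | 8.4% | 6.6% | 4.3% |
| 0.02 | 9.2% | 9.9% | 8.1% | 5.4% |
| 0.05 | 9.7% | 10.2% | 7.8% | 4.6% |
| 0.08 | – | 9.6% | 7.5% | 4.4% |

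In the balanced case ML with a t₂₂ critical value gives 6.5% at ICC 0.01 and 8.1% at 0.05. REML with z gives 5.6–6.8% with unequal sizes, so most of the excess comes from the estimator and the rest from the reference distribution.

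**Step 4: other readings of the model.**
- No school covariates (Model 1 in 6.3), ML + z, ICC 0.01–0.08: 6.7–7.4% balanced, 7.0–7.8% unequal.
- Seven school-level parameters (for example region and free-school-meal level fully crossed), ML + z: 9.9–12.0% unequal.
- Three-wave model with a constant arm term, five parameters, no school-by-time variance, ML + z: 9.3–9.6%.
- Three-wave model with treatment coded only after baseline, no school-by-time variance: 5.8–6.5%.

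The three-wave runs (2,000 per cell, error about ±1.3 points near 10%) assume a within-teacher correlation of 0.6, which the SAP does not give. Sex, experience and incomplete waves were left out; they should matter little for school-level degrees of freedom.

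**The case against.** The SAP fixes neither the reference distribution nor how treatment is coded across the three waves. The sentence that names maximum likelihood is about missing data, and what it says about MAR is not wrong. The pilot ICC is 0.01 with an interval reaching 0.00, where the inflation is modest or absent. All of this stands, and it makes any single error rate conditional.

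A reader might infer that the true type I error simply is 8–10%, nearly double the nominal level. The document does not support that. The range needs Wald z, a constant arm term, the additive strata and an ICC of at least 0.01. Near-doubling needs an ICC of about 0.02 or more; at the pilot value the ratio is about 1.6.

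A reader might also extend the point to every individual-level secondary outcome. Section 6.3 states maximum likelihood only for outcomes measured at all three waves and names no estimator for student outcomes measured twice. No logistic, ordinal or robust-error model was computed here. That ordinary cluster-robust errors run low with 24 clusters is a general property, and no figure is attached to it.

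Lastly, the sample size and the analysis section might be read as contradicting each other. Only the 68% figure clearly separates t from normal, and silence on degrees of freedom is not a contradiction. The fair statement is that planning appears to have allowed for few clusters and the analysis text does not carry this through.

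**Conclusion.** The concern holds in conditional form. The SAP names an estimator that understates between-school variance with 24 schools, and it states nothing to offset this. With Wald z, a constant arm term and additive strata, type I error is about 8% at ICC 0.01 and 9–10% at ICC 0.02–0.08, and the correct interval is about 20% wider at ICC 0.05.

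The excess falls to about 6.5–8% if a t reference is used with maximum likelihood. It falls to about 6% if treatment is coded only after baseline and schools do not vary over time. It is little or nothing as the ICC approaches 0. For ICC of 0.01 or more, every maximum likelihood reading with five or more school-level parameters was above 5%, so the direction is secure even though the size is not.

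One limit on the remedy: with post-baseline coding, if 30% of the school variance were school-by-time variance, which the model omits, the simulated error was 8.9% at ICC 0.01 and 26% at ICC 0.05. That share is an assumption. A degrees-of-freedom method cannot supply a missing variance component, so this is a separate question from the estimator.

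**What to change.** - In 6.2 and 6.3, specify REML with Kenward-Roger or Satterthwaite degrees of freedom for the linear mixed models (in Stata, `mixed` with `reml dfmethod(kroger)`). REML is likelihood-based, so the MAR justification carries over.
- State how treatment is coded across baseline, T1 and T2, so that the relevant degrees of freedom are clear.
- For the logistic and ordinal mixed models, use a t reference with between-school degrees of freedom.
- In 3.3 and 6.2, require a small-sample correction with matching degrees of freedom (for example of the CR2 type) if the robust-error fallback is used.

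The cost is SAP wording and a model option; no new schools or data are needed. Intervals become wider, by about 20% at ICC 0.05 compared with ML and z. The test becomes somewhat conservative at very low ICC: REML with t₁₉ gave 4.5% at ICC 0.01, 3.9% at 0.005 and 2.9% at 0 in the balanced case. Power at ICC 0.05 is about 82.8% with 19 df against 83.4% with 22, still above 80%. Only REML with t₁₉ was simulated; Kenward-Roger, Satterthwaite and CR2 were not.
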